### **5.3.1 Assessment of symptomatic intracranial haemorrhage (sICH)**

According to this protocol, sICH (ECASS III criteria) is defined as: any apparently extravascular blood in the brain or within the cranium that was associated with clinical

deterioration (defined by an increase in the NIHSS score of 4 or more points), or that led to death and that was identified as the predominant cause of the neurological deterioration. sICH event will be firstly evaluated by investigator. The DMC consultants will evaluate all the patients with NIHSS score increase of at least 4 any time after treatment (including all the sICH events evaluated by investigator).

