## **10. APPENDICES**

### **10.1 NATIONAL INSTITIUE OF HEALTH STROKE SCOR, NIHSS**

1a. Level of consciousness	0	Alert	
	1	Not alert, but arousable with minimal stimulation	
	2	Not alert, requires repeated stimulation to attend	
	3	Coma	
1b. Ask patient the month and their age	0	Answers both correctly	
	1	Answers one correctly	
	2	Both incorrect	
1c. Ask patient to open/close eyes and form/release fist	0	Obey both correctly	
	1	Obeyrs one correctly	
	2	Both incorrect	
2. Best gaze (only horisontal eye movements)	0	Normal	
	1	Partial gaze palsy	
	2	Forced gaze deviation	
3. Visual field testing	0	No visual field loss	
	1	Partial hemianopsia	
	2	Complete hemianopsia	
	3	Bilateral hemianopsia (blind, incl. Cortical blindness)	
4. Facial paresis (Ask patient to show teeth or raise eyebrows and close eyes tightly)	0	Normal symmetrical movement	
	1	Minor paralysis (flattened nasolabial fold, asymmetry on)	
	2	Partial paralysis (total or near total paralysis of lower face)	
	3	Complete paralysis of one or both sides (abscence of facial movement in the upper and lower face)	
5a. Motor Function - right arm	0	Normal (extends arm 90° or 45° for 10 sec without drift)	
	1	Drift	
	2	Some effort against gravity	
	3	No effort against gravity	
	4	No movement	
	9	Untestable (joint fused or limb amputated)	
5b. Motor Function - left arm	0	Normal (extends arm 90° or 45° for 10 sec without drift)	
	1	Drift	
	2	Some effort against gravity	
	3	No effort against gravity	
	4	No movement	
	9	Untestable (joint fused or limb amputated)	
6a. Motor Function -right leg	0	Normal (holds leg in 30° position for 5 sec without drift)	
	1	Drift	
	2	Some effort against gravity	
	3	No effort against gravity	
	4	No movement	
	9	Untestable (joint fused or limb amputated)	
6b. Motor Function -left leg	0	Normal (holds leg in 30° position for 5 sec without drift)	
	1	Drift	
	2	Some effort against gravity	
	3	No effort against gravity	
	4	No movement	
	9	Untestable (joint fused or limb amputated)	
7. Limb ataxia	0	No ataxia	
	1	Present in one limb	
	2	Present in two limbs	

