8. Sensory (use pinprick to test arms, legs trunk and face, compare side to side)	0	Normal	
	1	Mild to moderate decrease in sensation	
	2	Severe to total sensory loss	

Proprietary confidential information © 2017 Boehringer Ingelheim International GmbH or one or more of its affiliated companies

9. Best language (describe picture, name items)	0	No aphasia	
	1	Mild to moderate aphasia	
	2	Severe aphasia	
	3	Mute	
10. Dysarthria (read several words)	0	Normal articulation	
	1	Mild to moderate slurring of words	
	2	Near unintelligible or unable to speak	
	9	Intubated or other physical barrier	
11. Extinction and inattention (use visual double stimulation or sensory double stimulation)	0	Normal	
	1	Inattention or extinction to bilateral simultaneous stimulation in one of the sensory modalities	
	2	Severe hemi-inattention or hemi-extinction to more than one modality	

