5.1 PRIMARY ENDPOINT(S)

The primary efficacy endpoint is the percentage of patients with mRS 0-1 (favourable outcome) at Visit 5 (i.e., Day 90) after stroke onset by face-to-face interview with patient. A patient is considered to be a mRS 0-1 responder (response value set to 1) if he/she obtained a response of 0 or 1 on the modified Rankin scale otherwise the response value will be set to 0.

The primary safety endpoint is the percentage of patients with symptomatic intracranial haemorrhage (sICH) centrally evaluated by DMC consultants according to ECASS III definition within the whole study period. ECASSIII definition is any apparently extravascular blood in the brain or within the cranium that was associated with clinical deterioration (defined by an increase in the National Institute of Health Stroke Scale (NIHSS) score of 4 or more points), or that led to death and that was identified as the predominant cause of the neurological deterioration.

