6.6 HANDLING OF MISSING DATA AND OUTLIERS

According to CTP, all efforts should be made to collect complete CRF information referring to all patients with drug administration. No missing values regarding vital status and intracranial bleeds are expected.

The missing values related to efficacy outcome parameters will be imputed according to the rules described below and listed in Table 6.6:1.

Baseline imputation

In case of missing data for baseline NIHSS, the baseline NIHSS will be imputed to the best possible score (0).

Post baseline imputations

WLOCF: Worst and last observation carried forward

- any missing data that is not due to death will be replaced by the last observation carried forward (LOCF) i.e., either Visit 4, Visit 3, Visit 2, Visit 1C, Visit 1B.
- if the missing data is due to death, the data will be replaced by the worst score: the highest possible score (42) for the NIHSS, the score of 6 (i.e. Dead) for the modified Rankin scale, the score of 5 (i.e. Dead) for the Glasgow outcome, the lowest score (0) for the Barthel index.

- if the patient status (i.e. alive yes/no) is missing, the data will be replaced by the worst score excluding death: the highest possible score (42) for the NIHSS, the score of 5 for the modified Rankin scale, the score of 4 for the Glasgow outcome, the lowest possible score (0) for the Barthel index.

When all post baseline measurements are missing, the imputation across visits will depend on survival status (dead/missing/alive, alive will be handled the same as missing in this scenario) as per definition above. These imputations will be used for the derived endpoints (e.g. dichotomized endpoint) as defined in [Section 5](#).

For multi items scales (NIHSS, Barthel index): Imputation will be performed in two steps:

- 1.) Individual items will be imputed following the LOCF or worst score
- 2.) Total score is calculated

When all post baseline measurements are missing, the individual values for post baseline measurements will stay missing and the imputation across visits will depend on survival status (dead/missing/alive, alive will be handled the same as missing in this scenario) as per definition above.

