In case of NIHSS missing at baseline and at all post baseline time points, then the individual values for post baseline measurements will stay missing and the total NIHSS score for all post baseline data will be imputed depending on survival status (dead/missing/alive, alive will be handled the same as missing in this scenario).

Barthel index is present only at Visit 4 and Visit 5. In case of missing items for the Barthel index at Visit 4, the worst value will be imputed for these items.

Furthermore, in cases where one of more individual items is missing, the total score must be set to missing for the observed case type of analysis.

Table 6.6:1 Handling of missing data

Endpoint	Baseline value	Baseline imputation value	Post-baseline value at visit	Patient dead/alive at visit	Post baseline imputation value at visit
modified Rankin scale			Available	Alive	NA
			Missing	Alive	LOCF or worst excluding death (5) if missing at Visit 4
			Missing	Dead	Worst (6)
			Missing	Missing	Worst excluding death (5)
Barthel Index			Available	Alive	NA
			Missing	Alive	LOCF or worst if missing at Visit 4
			Missing	Dead	Worst (0)
			Missing	Missing	Worst (0)
Glasgow outcome			Available	Alive	NA
			Missing	Alive	Worst excluding death (4)
			Missing	Dead	Worst (5)
			Missing	Missing	Worst excluding death (4)
NIHSS total score	Available or missing	If missing impute best value (0)	Available	Alive	NA
	Available or missing	If missing impute best value (0)	Missing	Alive	LOCF or worst (42) if all post-baseline were missing
	Available or missing	If missing impute best value (0)	Missing	Dead	Worst (42)
	Available or missing	If missing impute best value (0)	Missing	Missing	Worst (42)

NIHSS Total score:

The total score of the NIHSS is the sum of the **15** individual item scores: level of consciousness (1), LOC questions (2), LOC commands (3), best gaze (4), visual (5), facial paresis (6), motor arm right (7), motor arm left (8), motor leg right (9), motor leg left (10), limb ataxia (11), sensory (12), best language (13), dysarthria (14), extension and inattention (15).

For the calculation of the total score:

The scores of '9' on motor (7-10) indicating amputation or joint fusion on motor arm right or left, motor leg right or left will be replaced by (4) for post baseline value and by best case (0) at baseline.

A score of '9' on dysarthria (14) will be replaced by the worst case value (2) for post baseline value and by best case (0) at baseline.

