This rule is to be applied for observed cases and WLOCF.

The censoring rules for time to death (survival time, [day]) at Day 90 and censoring flag will be calculated as following manner:

➤ **for a dead patient:**

death=yes

censoring flag=0

survival time=date of death – date of start bolus +1

if survival time >90 (patient alive at Visit5)

then death=no, censoring flag=1, survival time=90

➤ **for patient alive at Visit 5:**

death=no

censoring flag=1

survival time= date of last contact – date of start bolus +1

if survival time>90 then survival time=90

➤ **for a lost to follow up patient:**

death = no

censoring flag=1

if « last date patient known to be alive » is known

then survival time= last date patient known to be alive – date of start bolus +1

if « last date patient known to be alive » is unknown

then survival time= date of last contact – date of start bolus +1

if survival time>90 then survival time=90

Date of last contact is the maximum of {date of last measurement or visit, date of trial completion, last available date from AE and last available date from CM}.

The censoring rules for time to death (survival time, [day]) overall study and censoring flag will be calculated as following manner:

All deaths are taken into account whatever their time of occurrence, and even if they occurred after the 97 days (90 days +7).

➤ **for a dead patient:**

death=yes
censoring flag=0
survival time=date of death – date of start bolus +1

➤ **for patient alive at Visit 5:**

death=no
censoring flag=1
survival time= date of last contact – date of start bolus +1

➤ **for a lost to follow up patient:**

death = no
censoring flag=1
if « last date patient known to be alive » is known
 then survival time= last date patient known to be alive – date of start bolus +1
if « last date patient known to be alive » is unknown
 then survival time= date of last contact – date of start bolus +1

Date of last contact is the maximum of {date of last measurement or visit, date of trial completion, last available date from AE and last available date from CM}.

The length of stay in hospital will be calculated as follows:

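### SAP 6.6 scores an untestable NIHSS item 0 at baseline but 4 (motor) or 2 (dysarthria) afterwards, so an unchanged patient shows an artificial rise and cannot reach NIHSS 0-1 or the global response

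*SAP*

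**What the plan says.** SAP 6.6 builds the NIHSS total from 15 item scores and gives a special rule for the code 9.

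- **Motor items (both arms, both legs).** A 9 stands for amputation or joint fusion, in the SAP and in Protocol 10.1. For the total score it "will be replaced by (4) for post baseline value and by best case (0) at baseline".
- **Dysarthria.** Protocol 10.1 labels the 9 as "Intubated or other physical barrier". It "will be replaced by the worst case value (2) for post baseline value and by best case (0) at baseline".
- **Scope.** "This rule is to be applied for observed cases and WLOCF". The observed-case sensitivity analysis therefore carries the same recoding as the imputed analysis.

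Two other parts of the plan use NIHSS. The secondary efficacy endpoint (Protocol 5.1.1.2, SAP 5.2.2) requires an NIHSS of 0 or 1 at Day 90 together with three other criteria, and SAP 7.5.2 also reports each component on its own. The sICH definition in Protocol 5.3.1 includes clinical deterioration, "defined by an increase in the NIHSS score of 4 or more points", and SAP 5.1 repeats it. The same size of increase sends a patient to the DMC consultants for central evaluation.

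**The concern.** An amputation or fused joint that predates the stroke is the same at Visit 1A and at Day 90. Scoring it as normal at the first visit and as complete loss of movement at every later one makes the derived total record a worsening that did not happen.

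The responder endpoints are the main thing at stake. A patient with such a limb who recovers completely is counted as a failure on NIHSS 0-1, and therefore on the global response, by construction. The trial has one arm and reports proportions with confidence intervals, so there is no control group in which the effect could cancel. No planned analysis is free of it either.

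**Working it through.** **Inputs.** Item maxima are from Protocol 10.1, replacement values from SAP 6.6, the responder cut (total of 0 or 1) from SAP 5.2.2, the deterioration threshold (4 or more) from Protocol 5.3.1, and the planned N of 120 from Protocol 7.7.

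**1. The plan's own figure.** The 15 item maxima, leaving out the 9 codes, are 3 + 2 + 2 + 2 + 3 + 3 + (4 × 4) + 2 + 2 + 3 + 2 + 2 = 42. This matches the maximum total in Protocol 5.2, so the scale is read correctly.

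**2. Artificial rise.** For an item untestable at both times with no true change, rise = post-baseline replacement − baseline replacement. The lowest Day 90 total is the sum of the post-baseline replacements, with every other item at 0.

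| Untestable at both times | Rise | Reaches 4? | Lowest Day 90 total | NIHSS 0-1 possible? |
|---|---|---|---|---|
| One motor item | 4 − 0 = 4 | yes | 4 | no |
| Two motor items | 8 − 0 = 8 | yes | 8 | no |
| Dysarthria only | 2 − 0 = 2 | no | 2 | no |
| One motor item and dysarthria | 6 − 0 = 6 | yes | 6 | no |

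Only motor items reach 4 unaided. Dysarthria would need 2 further genuine points (2 + 2 = 4).

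**3. Effect on the rates.** One patient wrongly counted as a non-responder moves a rate by 1/120 = 0.83 percentage points. The documents do not say how many patients will have such an item. Assuming 0 to 2, the shift runs from 0 to 2/120 = 1.67 points. For the global response this is an upper limit, since the patient must also have met the mRS, Barthel and Glasgow criteria.

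**4. Alternatives for an item coded 9 at both times.**

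- Scored 0 at both: rise 0 − 0 = 0, lowest total 0, NIHSS 0-1 possible.
- Worst value at both: rise 4 − 4 = 0 (or 2 − 2 = 0), lowest total 4 (or 2), NIHSS 0-1 still impossible.
- Left as recorded: rise 9 − 9 = 0.

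Equal scoring alone removes the rise. Only excluding the item, or scoring it 0, also restores the responder criterion.

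**The case against.** The best defence is that the rule is conservative. It can only lower the NIHSS and global response rates. Those are secondary, are reported as a proportion with a confidence interval and no visible test, and sit beside mRS, Barthel and Glasgow components that the rule does not touch. Scoring a 9 as 0 is also the favourable choice in an open-label single-arm trial. The worst value is reasonable for an item that was testable at baseline and became untestable later; a new intubation, for instance, may reflect real worsening. All of that stands and limits the weight of the point. It does not justify scoring an unchanged limb in two ways.

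Three stronger readings are tempting, and the documents do not support them.

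- **False sICH events.** Because a motor item gives exactly 4 points, a reader might infer that the rule could add an event, for example moving 3/120 (2.5%) to 4/120 (3.3%). But sICH also needs extravascular blood, and haemorrhage as the predominant cause. It is judged by the investigator and then by the DMC consultants. SAP 6.6 introduces its imputation rules for efficacy outcomes, and neither document says that adjudicators use this derived total. At most, if they did, an unchanged patient could be sent for review needlessly.
- **The missing-baseline rule does the same harm.** SAP 6.6 sets a missing baseline NIHSS to 0. The responder endpoints use only the Day 90 score, and carry-forward draws only on post-baseline visits, so that 0 never enters them.
- **NIHSS change results are distorted.** Any change computed from the derived total would carry the rise, but the readable text contains no NIHSS-change endpoint.

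**Conclusion.** The point holds as a minor one. The SAP states a rule that gives a wrong result for a patient whose item is untestable both before treatment and at follow-up: a rise of 4 per motor item or 2 for dysarthria, and certain failure on NIHSS 0-1 and the global response in both the observed-case and the imputed analyses.

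The conclusion assumes that the item is coded 9 at both times and that the patient would otherwise have met the criteria. The number of such patients is an assumption and is likely to be very small. The mRS 0-1 analysis, its test against 40% and the sample size do not depend on the rule. For sICH, the documents support only a request to say which NIHSS score is used.

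**What to change.** In SAP 6.6:

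1. Exclude from the total (score 0), at every visit, an item coded 9 at baseline and still coded 9 later.
2. Keep the worst-case value (4 for motor items, 2 for dysarthria) only for an item testable at baseline that becomes untestable afterwards.
3. State that sICH review and adjudication use the recorded NIHSS, not this derived total. The ECASS III definition in the protocol stays as it is.

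The cost is a few sentences and a small programming change, with no new data. The one drawback is that the responder rates become slightly less conservative. Reporting the present worst-case rule as a sensitivity analysis covers that.

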### **6.2.3      Observation Period and Trial Completion**

A physical examination, the documentation of adverse events and of concomitant medication will be performed for all patients at all predefined treatment time points (Visit 1B and Visit 1C) as of the administration day and visit 2,3,4, and 5.

Lab test at visit 1A and visit 3 are mandatory. It will be optional at visit 2 and visit 5 in case of clinical deterioration (considered by investigator)

At visit 1B (i.e., 1 hour after the start of infusion of study drug), vital signs will be measured every 30 minutes until Hour 2. An 12-lead ECG recording will be made.

At visit 1C (i.e., 2 hours after the start of infusion of study drug), the NIH Stroke Scale will be performed. Vital signs will be measured every 30 minutes for 6 hours, then hourly until 24 hours. An 12-lead An 12-lead ECG recording will be made.

At visit 2 (24 hours), vital signs will be measured. The NIH Stroke Scale will be performed. A second imaging (CT/MRI) scan will be done within Hour 22 and Hour 36 after start of infusion of study drug.

At visit 3 (on day 7), vital signs will be measured. The NIH Stroke Scale will be performed. An 12-lead ECG recording will be made. A CT/MRI scan will be performed in case of clinical deterioration

At visit 4 (on day 30), vital sign will be measured. The NIH Stroke Scale, the modified Rankin Scale, and the Barthel Index will be performed. A CT/MRI scan will be performed in case of clinical deterioration.

At visit 5 (on day 90), vital sign will be measured. The NIH Stroke Scale, the Glasgow Outcome Score, the modified Rankin Scale, and the Barthel Index will be performed. A physical examination takes place. The patient termination record will be filled in. Length of stay in hospital will be assessed as well.

The trial completion (end of the trial) eCRF page has to be filled-in when patient has terminated the trial.

The end of the trial is:

- At the end of visit 5(Day 90 per protocol) for patients who have completed the trial on treatment and came to future visits as planned.
- After early discontinuation, if a patient refuses to attend future visits as originally planned.

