The length of stay in hospital is expressed in days and is equal to the date of discharge date and time is approximated to 23h O'clock for the end of day minus the date and time of the start of bolus. Because the date in SAS are expressed in seconds, the results will be divided by 86400 (24*60*60) in order to obtain a results expressed in number of days. The exact time of day of when the discharge time occurred is fixed at 23H59 PM for all patients (exact time not recorded in CRF).

Example: Start of bolus: 23/01/03 12H00 and date of discharge: 30/01/03

The length of stay in hospital will be: date of discharge (30/01/03, 23H59) - date of bolus (23/01/03, 12H00) / 86400 = 7.5 days.

Missing or incomplete AE onset dates are imputed according to BI standards [27, 27].

Missing or incomplete concomitant therapy onset dates are also imputed referring to AE standards. The end dates of missing or incomplete AE and concomitant therapy will be not imputed.

Trial completion is defined as the patients who are treated and completed Day 90 visit (i.e. Visit 5).

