6.7 BASELINE, TIME WINDOWS AND CALCULATED VISITS

The table below presents the visit structure according to the study flowchart depending on the time window scheduled in the CTP.

Table 6.7: 1 Visit structure

Period	Baseline	Trial drug admin.	On-treatment & Post-treatment					
Visit number per protocol	V1A		V1B#	V1C#	V2	V3	V4	V5
Planned study window	-4.5-0 hour	↔x→ 60 mins	1 hour ± 15 mins	2 hrs ± 30 mins	24 hrs ± 2hr	7 days ± 3 day	30 days ± 3 days	90 days ± 7 days
Study Day	← D0 →			D1	D7	D30	D90	
Visit description*	Baseline		Day0 (1H)	Day0 (2 H)	Day1	Day7	Day30	Day90

*label to be used in tables.

‘Baseline’ is defined as from enrolled in this study to the start time of bolus treatment administration

‘Study Day’ is calculated from the date & time of starting bolus treatment administration.

date & time is calculated from the date & time of starting infusion treatment administration.

Start of treatment:

The start of treatment (used for survival start time, length of stay in hospital, treatment at onset for adverse event) will be the **start of bolus treatment administration**; end of treatment is the end of infusion/drug/treatment administration.

Baseline value:

The baseline value will be the value recorded at V1A (last available value before the start of bolus treatment).

Change from baseline:

The change from baseline for any efficacy or safety endpoints (Vital signs) will be calculated as: value after baseline – value at baseline (V1A).

All efficacy analyses will be based on ‘nominal visits’ (CRF raw data visit) which will be labelled as indicated in the ‘Visit description’ row in tables, listings and graphs.

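### Length of stay runs from the exact bolus time to 23:59 on the discharge date, so on the SAP's own definition it can only be overstated, by about half a day on average under assumed discharge times

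*SAP*

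**What the plan says.** Protocol section 6.2.3 introduces the variable among the Visit 5 procedures: "Length of stay in hospital will be assessed as well". It is not among the efficacy or safety endpoints in Protocol section 5.1 or SAP sections 5.1 and 5.2.

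The derivation is in SAP section 6.6:

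- **End of the interval.** "The exact time of day of when the discharge time occurred is fixed at 23H59 PM for all patients (exact time not recorded in CRF"). An earlier sentence in the same paragraph says instead that the "time is approximated to 23h O'clock for the end of day".
- **Unit.** The difference is taken in seconds, and "the results will be divided by 86400 (24*60*60) in order to obtain a results expressed in number of days". Fractions of a day are kept.
- **Worked example.** "Example: Start of bolus: 23/01/03 12H00 and date of discharge: 30/01/03". The result is given as "date of discharge (30/01/03, 23H59) - date of bolus (23/01/03, 12H00) / 86400 = 7.5 days".

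SAP section 6.7 confirms the origin: "The start of treatment (used for survival start time, length of stay in hospital, treatment at onset for adverse event) will be the" (it then names the moment at which the bolus begins).

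The visible text contains no midpoint convention, whole-day rule or other correction for the missing discharge time. It also has no section on how length of stay will be summarised. Parts of the SAP's contents list are blank, so that section may simply not be visible, and its absence is not counted as a fault here.

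**The concern.** The two ends of the interval are treated differently. The bolus time is an observed clock time. The discharge time is set to the latest value compatible with the recorded date. An imputation at the extreme of the possible range does not produce errors that cancel across patients. Every error has the same sign, so the mean moves up and the median cannot move down.

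Fractional days add to the problem. A value of 7.5 days looks precise to a tenth of a day, although the discharge is known only to the day. SAP section 7 asks for summary statistics with one more decimal place than the listed data, which would carry this further if applied here.

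What is at stake is the absolute figure for hospital stay, and any reading of it against registries or other trials that count stay differently.

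**Working it through.** **Inputs from the documents.** Bolus at 12:00 on 23/01/03, discharge date 30/01/03, imputed discharge time 23:59 (or 23:00 in the other wording), divisor 86400 seconds, stated result 7.5 days (all SAP 6.6). Treatment starts 3 to 4.5 hours after stroke onset (Protocol 3.3.2, inclusion criterion 5).

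**Input not in the documents.** The true time of day of discharge. It is treated below as an assumption over a range.

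**Step 1: reproduce the SAP's figure.**

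- With 23:59: 7 days + 11 h 59 min = 7 + 11.983/24 = 7.4993 days, which rounds to the stated 7.5.
- With 23:00: 7 + 11/24 = 7.4583 days, which also rounds to 7.5.
- The two wordings differ by 59 min, or 0.04 day.

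**Step 2: error for one patient.** Overstatement = (23:59 − true discharge time)/24 h. No discharge can fall after 23:59 on its own date, so the value is at least 0. Its maximum, for a discharge at 00:00, is 23.983/24 = 0.999 day.

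Applied to the SAP's example:

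| Assumed discharge | Stay (days) | Overstatement (days) |
|---|---|---|
| 08:00 | 6.83 | 0.67 |
| 10:00 | 6.92 | 0.58 |
| 12:00 | 7.00 | 0.50 |
| 14:00 | 7.08 | 0.42 |
| 18:00 | 7.25 | 0.25 |

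**Step 3: mean error.** Mean overstatement = (23.983 − mean discharge hour)/24.

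| Assumed discharge times (uniform) | Mean hour | Mean overstatement (days) |
|---|---|---|
| whole day | 11.99 | 0.50 |
| 08:00 to 18:00 | 13 | 10.983/24 = 0.46 |
| 08:00 to 12:00 | 10 | 13.983/24 = 0.58 |
| 12:00 to 18:00 | 15 | 8.983/24 = 0.37 |

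**Step 4: if stay is counted from admission.** Starting the clock at bolus leaves out hospital time before treatment. For a stroke that began outside hospital, that time is at most 4.5 h, or 4.5/24 = 0.19 day. At this limit the net mean overstatement is 0.50 − 0.19 = 0.31 day (uniform over the day) or 0.46 − 0.19 = 0.27 day (08:00 to 18:00). If every discharge fell between 12:00 and 18:00 it would be 0.374 − 0.188 = 0.19 day. The two effects cancel for a discharge at 23:59 minus 4.5 h = 19:29, and a later discharge would be understated.

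**Step 5: check the alternatives.**

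- *12:00 imputation.* The error per patient is at most half a day in either direction. The mean error is (12 − mean discharge hour)/24: about 0.00, −0.04, +0.08 and −0.13 day for the four assumptions in step 3. A bolus at 15:00 with discharge the same day would give (12 − 15)/24 = −0.125 day, which is impossible, so a floor at zero is needed.
- *Whole calendar days.* The example gives 30/01 − 23/01 = 7 days, and the result is never negative. The error is (bolus hour − discharge hour)/24, which can have either sign. A bolus at 02:00 with discharge at 16:00 is understated by 14/24 = 0.58 day.

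**The case against.** The strongest defence is that this is a declared convention for a minor variable. The SAP calls the time an approximation, gives the reason and works an example, so a careful reader can see that the figure runs to the end of the discharge day. Counting the last day in full also resembles the survival-time rule in the same section, which subtracts dates and adds one. The variable is outside the primary and secondary endpoints, and a single-arm trial has no between-group contrast to distort. The 23:59 rule has the merit of never giving a negative stay, and neither alternative is free of error.

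Most of this stands, and it limits how much the point matters. It does not remove the bias: disclosing a one-sided rule leaves it one-sided. The survival rule works in whole days and does not combine an exact start with an end-of-day stop.

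A reader might go further than the documents allow in three ways:

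- **That every hospital stay is overstated.** This holds from bolus, apart from a discharge at exactly 23:59. It does not hold from admission, where the offset in step 4 applies.
- **That half a day, or a percentage such as 6.5% (0.46/7.04 for the SAP's example with a 13:00 discharge), is an established figure.** Both depend on assumed discharge times, and the example is an illustration rather than trial data.
- **That the two imputed times in the paragraph are a substantive conflict.** They differ by 0.04 day, both give 7.5, and the explicit rule and the example both use 23:59. It is a wording slip.

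**Conclusion.** The point holds within limits. On the SAP's bolus-to-discharge definition, the direction of the error follows from the text alone: 0 to just under 1 day per patient, never negative. Its average size is conditional: 0.50 day for discharges uniform over the day, and 0.37 to 0.58 day for the daytime ranges tried. Against an admission-to-discharge stay, the net mean is about 0.3 day at the 4.5-hour limit under the whole-day or 08:00 to 18:00 assumption, and lower if discharges are confined to the afternoon.

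A reader might infer that the trial's conclusions are affected. The documents do not support that. The test against a 40% response rate, the interim rules and the sICH estimate do not use length of stay, and no stated decision or external comparison depends on it. This is a low-priority correction to the absolute value of a descriptive figure.

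**What to change.** In SAP section 6.6, do one of the following:

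1. Report length of stay in whole calendar days, as discharge date minus bolus date. This matches the resolution at which discharge is recorded.
2. Keep fractional days but impute discharge at 12:00, with a floor at zero for patients who leave on the bolus day.

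In either case, remove the conflicting 23h wording, so that the paragraph carries one rule and an example that follows it.

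The cost is a line of text and a line of code, with no new data. The figure would no longer be comparable with any earlier report that used 23:59. Whole days also discard the recorded bolus time, so individual values can err in either direction. If comparability decides the matter and 23:59 stays, name the variable in tables and text as time from bolus to the end of the discharge day.
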